8. DATA MANAGEMENT

8.1 Fill in CRF

Protocol Version: 00

The case report form (CRF) is the primary data collection instrument for the study. All data requested on the CRF must be recorded. All missing data must be explained. If a space on the CRF is left blank because the procedure was not done or the question was not asked, write “N/D”. If the item is not applicable to the individual case, write “N/A”. All entries should be printed legibly in black ink. If any entry error has been made, to correct such an error, draw a single straight line through the incorrect entry and enter the correct data above it. All such changes must be initialed and dated. **DO NOT ERASE, OVERWRITE, OR USE CORRECTION FLUID OR TAPE ON THE ORIGINAL.**

8.2 Data Entry and Amendment

The data administrator, appointed by the sponsor, is responsible for data entry and management. All study data will be entered on the EpiData 3.1 Software. To vouch for the accuracy of the data, the data should be entered by two data entry staff to create duplicate copies, then the data administrator conducts proofing, scanning, and reporting on two copies of the database.

For existing CRE questions, data management will produce a question-and-answer form and request it from the investigator through the clinical monitor. The investigator should answer the questions and return as quickly as possible. Data management conducts data amending, affirming, and inputting according to the investigator's responses. It could revert to a question-and-answer format if necessary.

8.3 Data Management Responsibilities

All source documents and laboratory reports must be reviewed by the clinical team and data entry staff to ensure they are accurate and complete. Adverse events must be graded, assessed for severity and causality, and reviewed by the site PI or designee.

Data collection is the responsibility of the clinical trial staff at the site under the supervision of the site PI. During the study, the investigator must maintain complete and accurate documentation.

The Data Coordinating Center will serve as the Statistical and Data Coordinating Center for this study and will be responsible for data management, quality review, analysis, and reporting of the study data.

9. DATA ANALYSIS AND STATISTICAL CONSIDERATIONS

9.1 Sample Size Assumptions

The sample size of the investigational product must be up to 44 cases, and the placebo must be 44 cases (total sample size 88 cases). In this way, it can be deduced that the treatment group's efficiency is better than that of the placebo group, assuming a 90% single-sided testing efficiency.

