5	Very Severe	Very marked plaque elevation, scaling, and/or erythema. Plaque elevation = very marked (very marked elevation typically with hard sharp edges) Scaling = very coarse (coarse, thick tenacious scale over most of all of the lesions; rough surface) Erythema = very severe (extreme red coloration; dusky to deep red coloration) Majority of lesions have individual scores for induration, erythema, scaling, BSA and Pruritus (as described above) that average 5.

Efficacy Evaluation:

Success = [Baseline (ISGA ≥ 2) – follow-up ISGA score] ≥ 2 , meaning:

- Patients with “mild” psoriasis become “clear”.
- Patients with “moderate” psoriasis become “clear” or “almost clear”.
- Patients with “severe” psoriasis become at least “mild”, if not “clear” or “almost clear”.
- Patients with “very severe” psoriasis become at least “moderate” if not mild to clear.

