9.2.3 Analysis Data Sets

- A. Intention-to-treat (ITT) Analysis should be defined as all subjects randomized and dispensed medication. Subjects should not be excluded from the ITT population for dropping out or failing to follow the protocol.
- B. Safety Analysis Sets are performed for all patients who underwent randomization and received at least 1 dose of study medication. So, with or without a test record, patients who experience adverse events should be included in the statistical analysis if they have received at least one dose of the study medication.

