9.2.4 Analysis Plan

The response to treatment with TC Cream will be assessed using an intention-to-treat (ITT) comparison with the placebo group (ratio of efficacy goals achieved).

The statistical analysis will be performed using a two-sided t-test with a 95% confidence interval (CI) for the difference in response rates between the two treatment groups (ITT, TC vs. Vehicle). A P value < 0.05 is considered to be statistically significant.

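### Section 9.1 states 90% power for a single-sided test with no alpha, response rates or dropout allowance, but the planned analysis is two-sided at 0.05

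*Combined protocol and SAP*

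**What the plan says.** Section 9.1 of the combined protocol and SAP is the only justification of the sample size. It sets 44 cases on TC Cream and 44 on placebo, 88 in total, from which "it can be deduced that the treatment group's efficiency is better than that of the placebo group", "assuming a 90% single-sided testing efficiency". It names no endpoint, alpha, response rate, difference, standard deviation or dropout rate.

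Section 9.2.4 plans a different test: "The statistical analysis will be performed using a two-sided t-test with a 95% confidence interval (CI) for the difference in response rates", and "A P value < 0.05 is considered to be statistically significant". The synopsis gives the same rule, a two-sided 95% interval with P < 0.05.

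Two other places bear on power. Section 5.1.1 makes the ISGA outcome binary: "Success = [Baseline (ISGA ≥ 2) – follow-up ISGA score] ≥ 2". Section 9.2.3 keeps dropouts in the analysis: "Subjects should not be excluded from the ITT population for dropping out or failing to follow the protocol". No section says how a missing outcome is to be scored.

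**The concern.** The power statement and the analysis plan describe different tests, and nothing elsewhere in the document reconciles them. A one-sided test at a given alpha has a lower critical value than a two-sided test at the same alpha. Power computed for the first therefore overstates power for the second.

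The statement also cannot be checked. Without an alpha and a pair of response rates, neither the 90% nor the 44 can be derived. Sections 3.4.5 and 7 allow withdrawal for many reasons, yet 44 per arm carries no visible allowance for it.

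At stake is how a null result would be read. With 88 subjects, a reader would take the chance of missing the assumed effect to be 10%. Under some readings of 9.1 it is materially higher.

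**Working it through.** **Inputs from the documents**
- n = 44 per arm, 1:1; 90%, single-sided (9.1). The word used is efficiency, so reading it as power is an interpretation.
- Two-sided test, P < 0.05 (synopsis and 9.2.4).
- Binary success, compared as response rates (5.1.1, 9.2.4).

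**Not in the documents, so assumed**
- One-sided sizing alpha: 0.025, 0.05 or 0.10.
- Response rates: illustrations only.
- Dropout: 10% in each arm, as an illustration.

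**Step 1. Reproduce the plan's figure.** This is not possible: no effect or alpha is given. The only route is to back-solve the effect that gives exactly 90% one-sided power at 44 per arm, then apply the planned test to that same effect.

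**Step 2. Normal approximation.** The back-solved effect has standardised size z(1 − α₁) + z(0.90). Power at two-sided 0.05 is Φ[z(1 − α₁) + 1.282 − 1.960].

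| One-sided α₁ | z(1 − α₁) + 1.282 | minus 1.960 | Two-sided 0.05 power |
|---|---|---|---|
| 0.025 | 3.242 | 1.282 | 90.0% |
| 0.05 | 2.926 | 0.966 | 83.3% |
| 0.10 | 2.563 | 0.603 | 72.7% |

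A noncentral t calculation (86 df) gives 90.0%, 83.1% and 72.1%. The pooled two-proportion formula gives 90.0%, 82.9% and 71.8%, the same for every vehicle rate tried from 2% to 40%. The loss therefore depends on alpha, not on the example rates.

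**Step 3. Example with response rates.** Power = Φ{[(p₂ − p₁)√n − z·s₀]/s₁}, where s₀ = √[2p̄(1 − p̄)], s₁ = √[p₁(1 − p₁) + p₂(1 − p₂)], p̄ is the mean of the two rates and √44 = 6.633.

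- 10% vs 35.6%: s₀ = 0.5933, s₁ = 0.5650, difference × √n = 1.698.
  - One-sided 0.05: (1.698 − 1.645 × 0.5933)/0.5650 = 1.278, power 90%.
  - Two-sided 0.05: (1.698 − 1.960 × 0.5933)/0.5650 = 0.947, power 83%.
- 10% vs 39%: s₀ = 0.6082, s₁ = 0.5726, difference × √n = 1.924.
  - Two-sided 0.05: (1.924 − 1.960 × 0.6082)/0.5726 = 1.28, power 90%.

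**Step 4. Dropout at an assumed 10%, two-sided 0.05.**

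- Dropouts counted as failures (both rates × 0.90, n stays 44):
  - 10% vs 35.6% becomes 9.0% vs 32.0%: (1.528 − 1.960 × 0.5711)/0.5474 = 0.747, power 77%.
  - 10% vs 39% becomes 9.0% vs 35.1%: (1.731 − 1.960 × 0.5863)/0.5565 = 1.046, power 85%.
- Dropouts lost from the analysis (n = 44 × 0.90 = 39.6), sizing at one-sided 0.05: 2.926 × √0.90 − 1.960 = 0.816, power 79%.

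**The case against.** The strongest reply is that there may be no loss at all. Section 9.1 states no alpha. One-sided 0.025 is exactly the favourable tail of the two-sided 0.05 test in 9.2.4, and at that level power stays at 90%. The 0.05 in the synopsis and 9.2.4 belongs to a two-sided test, so carrying it over to a one-sided sizing is inference. This stands. A reader might infer that 44 per arm delivers 83% power, or that the true miss rate is 17%. The documents do not support that, because both figures require one-sided 0.05. That is a plausible reading, since 0.05 is the only significance level in the document, but it is not a stated one.

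A related reply is that even the 90% is power at an unknown effect, so actual power at 44 per arm cannot be computed in either direction. This also stands. It makes the missing assumptions at least as basic a defect as the mismatch in sidedness.

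A reader might also take the dropout figures as consequences of the plan. They are not. The plan keeps dropouts in the ITT set but does not say they count as failures, and the 10% is my illustration.

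Finally, the mismatch leaves the type I error and validity of the planned test alone: the two-sided rule in 9.2.4 is clear. That is correct, and it limits the repair to the power statement. It does not rescue the statement. Even if one-sided 0.025 was meant, 9.1 does not say so, and a reader cannot tell which power applies.

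**Conclusion.** The inconsistency is certain: 9.1 states power for a single-sided test, while the synopsis and 9.2.4 specify a two-sided one. It is also certain that 9.1 lacks the alpha, response rates and dropout allowance needed to check it.

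The size is conditional. Reading efficiency as power and holding the effect fixed, power for the planned test is 90%, about 83% or about 72-73% according to whether the sizing alpha was one-sided 0.025, 0.05 or 0.10. Under the 0.05 assumption, 10% dropout would bring it to about 77% if dropouts count as failures (10% vs 35.6% example) or about 79% if they are lost from the analysis. It is not established that the trial is underpowered, only that its stated power is not for the planned test and cannot be verified.

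**What to change.** Keep N = 88 and the two-sided analysis. In 9.1, delete the single-sided wording and restate the calculation for the two-sided 0.05 test of the ISGA success rate at Week 8. Give:
- the sponsor's assumed response rates in each arm;
- the assumed dropout rate;
- the rule for missing outcomes, which should also appear in 9.2;
- the power that results.

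An illustration, with rates to be replaced by the sponsor's own: *With 44 subjects per arm and a two-sided 0.05 test of Week 8 ISGA success, power is 90% for 10% vs 39% and 83% for 10% vs 35.6%. With 10% of subjects dropping out and counted as failures, these become about 85% and 77%.*

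The cost is one paragraph in 9.1 and a sentence on missing outcomes. No extra subjects are needed and the test does not change. The downside is that the stated power may become less favourable than 90%.

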9.2 Data Analysis Considerations

9.2.1 Efficacy Analysis Populations

The populations include all patients who were randomized and received at least one dose of any study drug.

9.2.2 Safety Analysis Populations

The populations include all patients who were randomized and received at least one dose of any study drug.

9.2.3 Analysis Data Sets

- A. Intention-to-treat (ITT) Analysis should be defined as all subjects randomized and dispensed medication. Subjects should not be excluded from the ITT population for dropping out or failing to follow the protocol.
- B. Safety Analysis Sets are performed for all patients who underwent randomization and received at least 1 dose of study medication. So, with or without a test record, patients who experience adverse events should be included in the statistical analysis if they have received at least one dose of the study medication.

9.2.4 Analysis Plan

The response to treatment with TC Cream will be assessed using an intention-to-treat (ITT) comparison with the placebo group (ratio of efficacy goals achieved).

The statistical analysis will be performed using a two-sided t-test with a 95% confidence interval (CI) for the difference in response rates between the two treatment groups (ITT, TC vs. Vehicle). A P value < 0.05 is considered to be statistically significant.

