	
 ○ Any types of investigational therapy for psoriasis within the last 30 days ✓ Within 3 months prior to randomization the patients have taken systemic treatment with retinoids or biological therapies (marketed or others) with a possible effect on psoriasis (e.g., alefacept, efalizumab, etanercept, infliximab). ✓ Planned initiation of, or changes to, concomitant medication that could affect psoriasis (e.g., beta blockers, anti-malaria drugs, lithium) during the double-blind phase of the study.
Endpoints	
Observation of Curative Effects:
 
 (1) Severity of local signs - Phenotypes 
 a. Induration (average over all lesions) b. Erythema (average over all lesions) c. Scaling (average over all lesions) (2) Extent - Body Surface Area (BSA) affected (3) Symptoms - Pruritus/itching (average over 24 hours) (4) Visual assessment: Digital photographs on the target skin lesion 
Note: (1) All patients will be examined and photographed before (first visit) and after (end of the curative treatment) treatment with TC Cream or placebo.
 
(2) The investigator(s) can, not must, consider enrolling the patients may have a lesion on elbow and/or knee. However, the patients who have no lesion on elbow or knee or only have a lesion on one of parts can be enrolled into this research.
 
Outcome Measures:
 
 • Primary Endpoint: 
 (1) Investigator's Static Global Assessment (ISGA) (2) Assessment of Targeted Lesions • Secondary Endpoint: 
 (1) PASI \geq 75% improvement • Tertiary Endpoint: 
 (1) Psoriasis Disability Index (PDI) (2) Dermatology Life Quality Index (DLQI) 
Statistical Analysis:
 
Comparison between two groups will be made using the t-test with two-sided 95% confidence interval (CI) for the difference in response rates between the two treatment groups (ITT, TC vs. Vehicle). A P-value < 0.05 is considered to be statistically significant.
 
Frequency of Evaluation:
 
 – 0 (before treatments), 2, 4, 6 and 8 weeks – After the initial 8 weeks of treatment, there will be a follow up period of 4 weeks during which no treatment is used.

Schematic Flow of Study Design

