3.1 Randomization

Subjects will be randomly assigned to a treatment agent according to a predetermined computer-generated randomization scheme.

Subjects will be assigned consecutive subject numbers in ascending order. This number will identify the subject and determine the treatment of drug product administration according to the randomization scheme.

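### Success rates are compared by an unadjusted t-test that leaves out baseline ISGA; a CMH test on a few baseline strata with a score-type interval would serve better, with a conditional power gain

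*Combined protocol and SAP*

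**What the plan says.** Section 9.2.4 sets the primary comparison: "The statistical analysis will be performed using a two-sided t-test with a 95% confidence interval (CI) for the difference in response rates", and "A P value < 0.05 is considered to be statistically significant". The statistical paragraph of the synopsis plans the same test. Neither place names a covariate, stratum or centre term, and Section 9.2.4.1 adds only descriptive summaries.

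The outcome is binary. Section 5.1.1 counts success as a fall of at least two ISGA grades, which it spells out by baseline grade; the first line reads "Patients with “mild” psoriasis become “clear". Section 5.1 gives another rule: a final score of 0 or 1 together with a two-grade improvement. Entry requires ISGA of at least 2 (Section 3.3.4), so baseline may be 2, 3, 4 or 5.

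On allocation, Section 3.1 says "Subjects will be randomly assigned to a treatment agent according to a predetermined computer-generated randomization scheme" and names no stratification factor. Section 9.1 gives "total sample size 88 cases", 44 per arm, "assuming a 90% single-sided testing efficiency". It states no response rates and no alpha.

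**The concern.** A t-test is a method for means. Applied to 0/1 data it estimates the variance from the observed proportions, so its interval can be too short, or collapse, when few patients respond. With 44 per arm and a vehicle control, a low response rate is possible.

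The plan also leaves unused a variable that it collects and that enters the endpoint definition. A mild patient must reach 0, while a moderate patient may stop at 1. If success differs much by baseline grade, chance imbalance in grade passes into the treatment difference, and an unadjusted test gives up power that a stratified test would keep.

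**Working it through.** **The plan's own figure.** The 44 per arm cannot be reproduced, because Section 9.1 gives neither response rates nor alpha. It can only be inverted. With pooled variance, power = Φ{[|p1 − p2|√n − z√(2p̄q̄)] / √(p1q1 + p2q2)}. Take n = 44, one-sided alpha 0.05 and 5% vs 27.6%. Then p̄ = 0.163, and [0.226 × 6.633 − 1.645 × √0.2729] / √0.2473 = 0.640 / 0.497 = 1.29, which gives power of about 90%. Starting from 10% on vehicle, the TC rate needed is 35.7%. Under a two-sided 0.05 test these pairs have about 83% power, so the one-sided wording of Section 9.1 and the two-sided wording of Section 9.2.4 also need reconciling.

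**Success rules side by side.**

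| Baseline ISGA | End score needed, Section 5.1.1 | End score needed, Section 5.1 |
|---|---|---|
| 2 | 0 | 0 |
| 3 | 0–1 | 0–1 |
| 4 | 0–2 | 0–1 |
| 5 | 0–3 | 0–1 |

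The rules agree for grades 2 and 3 and conflict for 4 and 5. Both make the required end score depend on baseline. Neither says how response rates differ by grade.

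**Test size.** All 45 × 45 = 2,025 outcomes at 44 per arm were enumerated. The pooled t-test (86 df, critical value 1.988) and the Pearson chi-square disagree in 4 of them. Type I error is the same for both: 1.0% at a common rate of 2%, 5.9% at 10%, 5.5% at 15%; the maximum is 6.0% for each.

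**Interval coverage.** The t-interval is d ± 1.988 × √(s² × 2/44), with s² = 44[p1q1 + p2q2]/86 at the observed proportions. Exact results:

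| TC vs vehicle | t-interval | Newcombe |
|---|---|---|
| 5% vs 1% | 89.1% | 99.5% |
| 10% vs 2% | 92.3% | 97.0% |
| 20% vs 2% | 94.0% | 96.8% |
| 27.6% vs 5% | 94.6% | – |
| 40% vs 10% | 94.9% | 95.3% |

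The first row can be explained directly. The chance of no responder in either arm is 0.95^44 × 0.99^44 = 0.105 × 0.643 = 6.7%. The interval then has zero width at 0 and misses the true 4-point difference. That is 6.7 of the 10.9 points of miscoverage.

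**Power of a stratified test.** CMH without continuity correction is [Σ(a − n1·m/N)]² / Σ[n1·n0·m(N − m)/(N²(N − 1))], summed over strata and compared with 3.84. Here a is TC successes, m all successes, n1 and n0 the arm sizes and N the stratum total. All rates and mixes below are assumptions, for baseline 2 / 3 / ≥4:

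- A: mix 35/40/25%, vehicle 2/10/35%, TC 10/40/75%. Averages: 0.007 + 0.040 + 0.0875 = 13.5% and 0.035 + 0.160 + 0.1875 = 38.3%.
- B: mix 30/50/20%, vehicle 3/12/30%, TC 12/45/65%.
- Flat: mix 35/40/25%, 10% vs 40% in every grade.

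Power from 40,000 simulated trials each (Monte Carlo standard error about 0.1 to 0.25 points):

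| Scenario | t-test | CMH, 2 vs ≥3 | CMH, 2 / 3 / ≥4 |
|---|---|---|---|
| A | 78.4% | 82.0% (+3.6) | 85.4% (+7.0) |
| B | 82.9% | 85.1% (+2.2) | 85.7% (+2.8) |
| Flat | 92.9% | 92.2% (−0.7) | 91.8% (−1.1) |

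Crossing the three strata with two centres (six strata, no centre effect) gives 83.7% in A, 84.6% in B and 90.8% when flat. The gains fall to about 5 points and 1 point, and the flat loss grows to about 2. A continuity correction on those six strata gives 75.1% and 76.8% in A and B, below the t-test.

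**The case against.** The case for leaving the plan alone is strong in parts. On 0/1 data with equal arms, the t-test is almost the chi-square test. A reader might infer that the planned test inflates the false-positive rate; the enumeration does not support that. The 5.9% reflects discreteness and is the same for an unadjusted chi-square. Nor is the interval generally invalid. It is close to nominal near the rates that 44 per arm could detect with high power. The clear shortfalls lie where t-test power is only 12% (5% vs 1%) and 38% (10% vs 2%), and Newcombe is conservative there.

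A reader might also infer that stratifying gains power at no cost because the endpoint makes baseline prognostic by construction. The documents do not support this either. The definition fixes the end score needed; how response varies by grade is empirical and undocumented. Scenarios A and B both assume success rising steeply with severity. Under the Section 5.1 rule, severe and very severe patients need drops of three and four grades, so the gradient could flatten or reverse. With an assumed inverted-U (vehicle 5/15/7%, TC 25/50/30%), three-stratum CMH goes from 87.9% to 87.8%.

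All of this stands and limits the point. It does not remove the low-rate failure of the interval, which would matter most if the trial disappoints and the interval becomes the main result. It also does not alter the asymmetry of a loss of about 1 point against a gain of 2 to 7.

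**Conclusion.** The point holds as a should-change on the choice of method. The plan analyses a binary endpoint with an unadjusted t-test and ignores a baseline grade that enters the definition of success. The defect in the interval is confined to low response rates: coverage of 89% to 92% in the two worst pairs tabulated, and about 94% to 95% in the others. The power consequence is conditional: about +2 to +7 points if baseline is strongly prognostic, and about −1 point if it is not, for CMH without continuity correction on two or three ISGA strata. The text of the plan and the exact coverage figures are firm. The size of the power gain is not, because it rests on assumed rates and an assumed baseline mix.

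**What to change.** 1. Reconcile the success rules in Sections 5.1 and 5.1.1 before choosing strata.
2. In Section 9.2.4 and the synopsis, replace the t-test with a CMH test of Week 8 ISGA success, without continuity correction, stratified by baseline ISGA in a few prespecified groups (for example 2 vs ≥3, or 2, 3, ≥4). Do not cross the strata with centre.
3. Report the risk difference with a score-type 95% interval (Newcombe or Miettinen-Nurminen), and state in advance whether it is stratified on the same groups. The Newcombe coverage above is for the unstratified form.
4. Optionally, use baseline-adjusted ANCOVA for PDI and DLQI.

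The cost is analysis wording only, since baseline ISGA is already collected, plus the roughly 1 point of power at risk if baseline proves not to be prognostic.

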
5. MEASUREMENT OF EFFECT

5.1 Clinical End Points

Clinical outcomes will be evaluated by following the criteria:

1. Primary Endpoint:
 - (1) Investigator's Static Global Assessment (ISGA)
 - (2) Assessment of Target Lesions
2. Secondary Endpoint:
 - (1) PASI \geq 75% improvement
3. Tertiary Endpoint:
 - (1) Psoriasis Disability Index (PDI)
 - (2) Dermatology Life Quality Index (DLQI).

For the purposes of this study, patients should be evaluated at baseline (0) and reevaluated for response at 2, 4, 6, and 8 weeks. In addition, a rebound evaluation should also be obtained 4 weeks after the final evaluation of week 8.

The efficacy evaluation of all outcomes will be static ordinal, integer-valued, and scaled (e.g., success or failure), where 'success' involves a score of Clear/Almost Clear and a 2-grade improvement.

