5.1.2 Target Lesion

Pre-select two target lesions representative of the disease (for example: one from a refractory area, elbow or knee, while the other from the trunk) for separate variables, including induration, erythema, scaling, and BSA on a 6-point score.

Take photographs and measure the severity and extent before the clinical intervention and at every visit.

Effective (average of 2 Target Lesions) = [Baseline (Target Lesions ≥ 2) - Target Lesions

Protocol Version: 00

score at end of treatment] ≥ 2 .

The response to TC Cream will be assessed relative to the placebo group (ratio of patients who achieved the efficacy goal).

Table 7. Severity of Psoriasis Area Severity Index (PASI) at the Target Lesion Site

Score	Grade	Erythema	Scaling	Plaque Elevation
0	Clear	No evidence of erythema	No evidence of scaling	No evidence of plaques above normal skin level
1	Almost Clear	Pink discoloration, minimal erythema	Occasional fine scales hardly noticeable	Slight, just discernable elevation above normal skin level
2	Mild	Light red coloration	Slight but definite roughness, fine scale present, no cracking	Discernable elevation above normal skin level upon examination, but not pronounced
3	Moderate	Moderate redness, but not dark	Moderate roughness, somewhat coarse scaling	Definite plaque formation with rounded/sloped edges to plaque
4	Severe	Dark red coloration	Marked roughness, coarse/thick scaling, cracking may be evident	Marked elevation with hard, distinct edges to plaque
5	Very Severe	Very dark red coloration with induration present	Very thick scales covering extensive area severe cracking/fissures may be evident	Very marked elevation, very hard and sharp edges to plaque

Note: Body Surface Area (BSA) percentage is no longer requested as an individual component sign in the PASI scale, but the BSA percentage and distribution should be recorded at baseline.

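### Two primary endpoints share one unadjusted 0.05 threshold with no success rule, and ISGA success has no named visit, so the false-positive rate is not controlled at 5%

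*Combined protocol and SAP*

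**What the plan says.** The Synopsis and section 5.1 put two items under the primary endpoint: the ISGA and "Assessment of Target Lesions". PASI 75 is secondary; PDI and DLQI are tertiary. Section 5.1 has patients "reevaluated for response at 2, 4, 6, and 8 weeks", with a further evaluation four weeks after Week 8.

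The inferential plan in 9.2.4 is one two-sided t-test with a 95% confidence interval for the difference in response rates, and the rule "A P value < 0.05 is considered to be statistically significant". Section 9.2.4.1 adds only descriptive summaries. No section gives a success rule, an order of testing, a split of alpha or an adjustment.

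Timing differs by endpoint. Section 5.1.2 takes target-lesion response at the end of treatment, and 5.1.3 takes PASI 75 after 8 weeks. Section 5.1.1 uses a follow-up ISGA score with no visit named.

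Two definitions conflict:
- **ISGA success.** Section 5.1 ties success to clear or almost clear together with a two-grade improvement. Section 5.1.1 needs only a drop of two grades, so it also counts severe to mild and very severe to moderate.
- **Target lesions.** Section 5.1.2 scores lesions "for separate variables, including induration, erythema, scaling, and BSA on a 6-point score". Its Table 7 has columns for erythema, scaling and plaque elevation only, with the note that "Body Surface Area (BSA) percentage is no longer requested as an individual component sign in the PASI scale".

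**The concern.** With two primary endpoints and no success rule, the trial's own criterion for success is left to be settled later, possibly with the data in view. Three rules fit the text: either endpoint, both endpoints, or ISGA at whichever visit is chosen plus target lesions. They differ several-fold in false-positive rate, and they also differ in power. A result of P < 0.05 on one endpoint and not on the other would have no agreed interpretation. The undated ISGA score adds a choice that the target-lesion and PASI 75 definitions do not have.

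**Working it through.** **Inputs from the document.** Two primary endpoints and four on-treatment visits (5.1); two-sided 0.05 per test (9.2.4); 44 per arm and 90% single-sided power (9.1). **Assumed.** The correlations between endpoints and between visits, and all response rates; the document gives none.

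**The plan's own figure.** Section 9.1 cannot be reproduced, because it states no alpha, response rates or endpoint. By the usual two-proportion formula with pooled variance under the null, 44 per arm has 90% power for an assumed 10% versus 35.7% at one-sided 0.05, or 10% versus 39.1% at two-sided 0.05. So the 90% cannot be assigned to either primary endpoint.

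**Either endpoint at Week 8.** Error = 0.05 + 0.05 − P(both significant), for correlated normal test statistics with both nulls true. The TC-only column is 0.025 + 0.025 − P(both significant in favour of TC).

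| Endpoint correlation | P(both), two-sided | Either, two-sided | Either, favouring TC |
|---|---|---|---|
| 0 | 0.0025 | 0.0975 | 0.0494 |
| 0.5 | 0.0093 | 0.0907 | 0.0454 |
| 0.7 | 0.0165 | 0.0835 | 0.0417 |
| 0.9 | 0.0296 | 0.0704 | 0.0352 |

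With the planned t-test on binary responses at 44 per arm, and assumed true rates of 5% to 30% equal in both arms, one test has an error of 4.8% to 5.9%. Either endpoint then gives about 8.4% to 11.4%, so the normal approximation does not overstate the problem.

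**ISGA at any on-treatment visit, or target lesions at end of treatment.** This is five tests. If independent, 1 − 0.95^5 = 22.6%. For correlated tests, I simulated with 2 million draws per setting. Visit correlation decays with distance, and the correlation between an earlier ISGA and the final target-lesion test is the product of the endpoint and visit correlations.

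| Endpoint correlation | Adjacent-visit correlation 0.5 | 0.7 | 0.8 |
|---|---|---|---|
| 0.5 | 20.1% | 17.9% | 16.3% |
| 0.7 | 19.4% | 17.2% | 15.5% |

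Over correlations of 0.5 to 0.9 for both, with either decaying or equal visit correlation, the range is about 11% to 20%.

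**Both endpoints required at Week 8.** A false claim needs significance on at least one endpoint whose null is true, so the error is at most 5%. With both nulls true it is the P(both) column, 0.25% to 3.0%. If each endpoint had 90% power (an assumption), joint power would be 0.9 × 0.9 = 81% at correlation 0, 83% at 0.5, 85% at 0.7 and 87% at 0.9.

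**The case against.** The strongest defence is that Week 8 is the natural reading. The objective is stated over 8 weeks, 5.1 treats Week 8 as the final evaluation before the rebound visit, and 9.2.4 names one comparison and no test by visit. Both scores also rest largely on redness, scale and elevation, so the correlation is probably high and the inflation nearer 7% than 10%. A sponsor could say that both endpoints were always meant to be required. These points reduce the likely size, but they do not supply the missing rule. Even at correlation 0.9, either-endpoint success exceeds 5%.

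Four stronger readings are tempting and do not hold.
- **That the error rate is simply well above 5%.** A reader might infer this, but it depends on the rule. If both must win, the error is at most 5%.
- **That both endpoints are open at all four visits, giving eight tests.** Section 5.1.2 fixes target lesions at the end of treatment. Only ISGA is undated, so at most five on-treatment tests are open. Evaluations are scheduled at each visit, but no section orders a test at each.
- **That including BSA demonstrably changes who counts as a responder.** The conflict is real, since BSA is listed as an item but has no column in Table 7. However, the note concerns BSA percentage in the PASI scale, and the only average that 5.1.2 defines is over two lesions. Any worked example needs a formula for combining the items that the plan does not give.
- **That a baseline target-lesion score of at least 2 must become an entry criterion.** The responder formula presupposes it and 3.3.4 does not state it, so a formal gap exists. But 3.3.4 already requires ISGA of at least 2 and two lesions suitable for evaluation, and nothing shows how often the gap would matter. A new criterion would also change who enters the trial.

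**Conclusion.** The concern holds in a conditional form. As written, the plan does not fix the false-positive rate at 5%, because neither the success rule nor the ISGA visit is specified. The size depends on the rule adopted:
- both endpoints at Week 8: at most 5%, with lower power than each endpoint alone;
- either endpoint at Week 8: about 7% to 10% two-sided, or 3.5% to 4.9% in favour of TC against a nominal 2.5%;
- ISGA at any on-treatment visit, or target lesions: about 15.5% to 20%, for endpoint correlation 0.5 to 0.7 and visit correlation 0.5 to 0.8.

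All correlations are assumptions. The joint power of 81% to 87% rests on 90% per endpoint, which 9.1 does not state. The two ISGA success definitions and the unclear target-lesion score add analytic freedom that these figures do not include.

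**What to change.** In 9.2.4, prespecify a fixed sequence, each step at two-sided 0.05 and tested only if the one before is significant:
1. ISGA success at Week 8, as the primary test.
2. Target-lesion response at Week 8.
3. PASI 75 at Week 8.

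Name Week 8 as the ISGA analysis visit in 5.1.1. Declare the other visits, the rebound evaluation, PDI and DLQI descriptive. Before unblinding, reconcile the ISGA success definitions in 5.1 and 5.1.1. Also state in 5.1.2 whether BSA enters the target-lesion score and how the items are combined.

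The cost is protocol wording, with no increase in sample size for multiplicity. The real price is that target-lesion response can no longer rescue a failed ISGA result. If the sponsor will not accept that, two alternatives also control the error. Requiring both endpoints lowers power. Testing each at 0.025 gives at most 5% (1 − 0.975² = 4.94% if independent), but keeping 90% power needs ((2.241 + 1.282)/(1.960 + 1.282))² = 1.18 times the sample, so 44 per arm becomes about 52.
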